1. To compare the efficacy in reducing the frequency of migraine attacks under prophylactic treatment with Memantine at a rate of 20 mg divided into two doses per day against sodium Valproate at a rate of 1000 mg divided into two doses per day for three months in adult patients with migraine.

B. Specific objectives

1. To evaluate the baseline frequency of migraine attacks in adult patients with migraine 28 days prior to the study.
2. To evaluate the frequency of migraine attacks of the group - treatment with sodium Valproate for three months, in adult patients with migraine.
3. To evaluate the frequency of migraine attacks of the group - treatment with Memantine for three months, in adult patients with migraine.

C. Secondary objectives

1. Evaluate the response rate to treatment.
2. Assess migraine disability using MIDAS (Migraine Disability Assessment) before and after treatment.
3. To assess pain intensity in migraine attacks with the visual analog scale (VAS) before and after treatment.
4. Identify adverse effects to sodium Valproate and Memantine.

SUBJECTS AND METHODS

Site

The study was conducted at the outpatient clinic of the Hospital Central [name] Prieto, San Luis Potosí.

Design

Prospective, randomized, double-blind, controlled clinical trial.

Inclusion criteria

1. Men and women from 18 to 65 years old.
2. Diagnosis of episodic migraine according to the ICHD-III of the IHS at least one year prior to the study.
3. Must present at ≥ 4 - ≤ 8 migraine attacks per month.
4. Not receiving prophylactic treatment for migraine headache.
5. Sign informed consent

Exclusion Criteria

1. Pregnant or breastfeeding patients.
2. Patients with other types of non-migraine headache.
3. Allergy to Sodium Valproate and/or Memantine
4. Being a carrier of systemic disease (infectious, immunological or metabolic processes) or cardiovascular disease (myocardial, coronary or valvular heart disease) that prevents participation in the study.

Elimination Criteria

1. Patients who do not tolerate the study drug during titration.
2. Patients who voluntarily leave the study.
3. Patients lost to follow-up.

Variables

Dependent's

1. Frequency of migraine attacks: Defined as the number of migraine attacks presented during the month. It is a continuous variable.
2. Treatment response rate: Defined as a decrease equal to or greater than 50% in the frequency of days with migraine compared to the baseline situation. It is a continuous variable.

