Recruitment was carried out from July 2019 to August 2020 in the outpatient service of Neurology, Referral and Emergency of the Central Hospital. Patients who met the inclusion criteria and signed the informed consent form participated in the study. At the time of recruitment, they will be randomized by computer by an external collaborator of wide experience, assigning them a number and an external collaborator will distribute them in one of the two groups. Double-blinding will be performed, both for the researcher and for the participant, the only one who knew which group they were assigned to was the one who performed the randomization.

A total of 4 visits were made, with a time interval of one month for each visit.

Visit 1 (Week 0): a clinical history was taken, a physical examination was performed, the informed consent form was signed (Annex 1), and the inclusion and exclusion criteria form (Annex 2) was filled out by the researcher. A "Migraine diary" (Annex 3) was provided to the patient where the migraine attacks were recorded to identify the baseline characteristics such as frequency, intensity, duration.

Visit 2 (Week 4): the patient was given the medication assigned by the corresponding randomization. Memantine or VPA was prescribed as an oral tablet at night for one week and then increased in the second week to one tablet in the morning and at night. The baseline MIDAS survey was performed to identify migraine disability. The baseline "Migraine Diary" was collected and a new "Migraine Diary" was provided.

Visit 3 (Week 8): Frequency of migraine attacks, adverse effects and tolerability of treatment were assessed by the investigator. The "Migraine Diary" was collected and a new "Migraine Diary" was provided. The corresponding medication was given for four weeks.

Visit 4 (Week 12): Visit 3 (Week 8): Migraine attack frequency, adverse effects and tolerability of treatment were assessed by the investigator. The "Migraine Diary" was collected and a new "Migraine Diary" was provided. The corresponding medication was given for four weeks.

Visit 5 (Week 16): Frequency of migraine attacks, adverse effects and tolerability of treatment were evaluated by the investigator. The "Migraine Diary" was collected. The MIDAS survey was performed again to assess post-treatment disability.

Financing

A donation of the pharmacological treatment Memantine and sodium Valproate was received from the Torrent Pharma Laboratory (Annex 5).

STATISTICAL ANALYSIS

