"Efficacy of Memantine compared to sodium Valproate as prophylactic treatment for Episodic Migraine" A controlled randomized pilot clinical trial

A controlled randomized clinical trial

NCT04698525

ID 74-19

Study Protocol document date: February 15, 2019.

Statistical Analysis Plan document date: January 15, 2020.

Informed Consent Form document date: February 15, 2019.

STATISTICAL ANALYSIS PLAN

Sample size calculation

Normal distribution model: $x=Z(c/100)^2 r(100-r)$. $n=N x / ((N-1)E^2 + x)$ $E=\text{Sqrt}[(N-n)x / n(N-1)]$. With a margin of error of 5%, a confidence level of 95%, with a prevalence of migraine in the general population of the State of San Luis Potosi of 271800 with a distribution response of 15%.¹⁹ The recommended sample size is 196 participants. Because a pilot study will be conducted, 10% of the sample size will be taken to make it representative, a sample size of 20 participants for each group is decided.²⁰

Descriptive statistical analysis of the variables of interest will be performed. For continuous variables, analysis will be performed using the student's t-test. The number of participants (n) and the final analysis was calculated using R (56). Alpha, the probability of type 1 error was set to 0.05 and the power was set to 0.8 which resulted in the probability of a type 2 error of 0.2, given that we limited to 20 participants per treatment, delta was estimated with this restriction.

The aim of this study was to assess the efficacy of memantine and compared sodium valproate in the prophylactic treatment of migraine.

Study design

A single center, doble-blinded, controlled, randomized pilot clinical trial. The present study was designed as a randomized, double-blind, controlled pilot trial. It was authorized by the Research and Ethic Committee in February 2019, with the ID 74-19 and register in Clinical Trials from INH with the NCT04698525.

The study was conducted from July 2019 to November 2020 at Neurology service at Hospital Central [name] Prieto, San Luis Potosí, México.

Inclusion criteria

Men and women from 18 to 65 years old.

Diagnosis of migraine according to the ICHD-III of the IHS at least one year before the study.

To have at least 4-14 migraine attacks per month.

Not receiving prophylactic treatment for migraine

Sign informed consent

Exclusion criteria

Pregnant or lactating patients.

Patients with another type of non-migraine headache.

Allergy to Sodium Valproate and/or Memantine

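### Randomisation at recruitment comes four weeks before the baseline diary is returned and the first drug given, so patients who leave or fall outside the attack range in that month can already be randomised

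*Protocol*

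**What the plan says.** The Protocol's Work Plan sets out the order of events.

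- Who takes part: "Patients who met the inclusion criteria and signed the informed consent form participated in the study".
- When they are allocated: "At the time of recruitment, they will be randomized by computer by an external collaborator of wide experience".
- Visit 1 (Week 0): consent is signed and "the inclusion and exclusion criteria form (Annex 2) was filled out by the researcher". Of the diary handed out then, the text says that it "was provided to the patient where the migraine attacks were recorded to identify the baseline characteristics such as frequency, intensity, duration".
- First drug, four weeks later: "Visit 2 (Week 4): the patient was given the medication assigned by the corresponding randomization". The baseline diary is collected at this visit, and "The baseline MIDAS survey was performed to identify migraine disability".

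The Protocol's inclusion criterion is "Must present at ≥ 4 - ≤ 8 migraine attacks per month"; the SAP's is "To have at least 4-14 migraine attacks per month". Neither criterion names the diary as the source of the count.

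The SAP's primary outcome is the between-group difference in change from baseline in monthly attack frequency, taken from the diary. The Protocol's Elimination Criteria remove patients who do not tolerate the drug during titration, who withdraw, or who are lost to follow-up. Neither document defines an analysis set.

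**The concern.** Consent and the eligibility form are Visit 1 events, so recruitment most naturally means Week 0. The Visit 2 text refers to an assignment already made. Allocation then comes before the month that supplies the baseline for the primary outcome and the only prospective count of attacks.

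Two kinds of patient can therefore be randomised who need not have been. One leaves between Week 0 and Week 4 without taking any drug, and the elimination criteria then turn that departure into a post-randomisation removal. The other qualifies by history but records a diary count outside the entry range, and neither document says what happens next. In a trial of 20 per group, with no stated allowance for dropout, each avoidable loss costs precision and leaves a gap between those randomised and those analysed.

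**Working it through.** **Planned sample size.** With Z = 1.96, r = 15, E = 5 and N = 271800, x = 1.96² × 15 × 85 = 4898.04 and n = 271800 × 4898.04 / (271799 × 25 + 4898.04) = 195.8. The stated 196 is reproduced. The formula has no term for losses or for the time of allocation, so moving randomisation changes neither 196 nor the 20 per group.

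**Timeline (Protocol, Work Plan).**

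| Event | Week |
|---|---|
| Consent, eligibility form, diary handed out | 0 |
| Randomisation, read as recruitment | 0 |
| Diary collected, baseline MIDAS, first drug | 4 |

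The gap is 4 − 0 = 4 weeks.

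**Losses (Protocol, Summary, Results and Discussion).** Memantine: 16 − 14 = 2, and 2/16 = 12.5%. Valproate: 17 − 13 = 4, and 4/17 = 23.5%. Together 6/33 = 18.2%: three lost to follow-up and three attributed to COVID-19. None is dated relative to first drug. If k of the six left before it, k runs from 0 to 6, or 0% to 18% of those randomised.

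**Where k probably lies.** If each patient contributes a whole number, a reported mean must equal a whole total divided by n.

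| Baseline mean | Arm | Fits | Does not fit completers |
|---|---|---|---|
| Attacks 5.31 | Memantine | 85/16 = 5.3125 | 74/14 = 5.286, 75/14 = 5.357 |
| Attacks 5.35 | Valproate | 91/17 = 5.353 | 69/13 = 5.308, 70/13 = 5.385 |
| VAS 8.94 | Valproate | 152/17 = 8.941, 143/16 = 8.938 | 116/13 = 8.923 |
| MIDAS 60.87 | Memantine | 974/16 = 60.875 if truncated, 913/15 = 60.867 if rounded | 852/14 = 60.857 |
| MIDAS 51.92 | Valproate | 675/13 = 51.923; also 623/12 = 51.917, or 727/14 = 51.929 if truncated | (fits completers; not 17: 882/17 = 51.882, 883/17 = 51.941) |

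The attack means fit the full arms, which points towards few or no early losses. Three cautions apply.

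- The Results describe the memantine pre-treatment attacks as covering three months, against a 28-day baseline in the Specific objectives. Their source is therefore unclear, and monthly averages need not be whole numbers.
- Truncation matters. Protocol Table 1 prints 4/17 = 23.529% as 23.52%, and a truncated 75/14 = 5.357 would also print as 5.35.
- Valproate baseline MIDAS, a Visit 2 measure, does not cover all 17. That is compatible with losses before Visit 2 and equally with completer-only reporting.

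**Was anyone out of range?** The summaries do not show it. Counts of 4, 5, 6, 7 and 8 attacks in 6, 6, 0, 1 and 3 patients total 85 and give SD 1.54. In 2, 11, 2, 0 and 2 patients they total 91 and give SD 1.11. Both match the reported figures with everyone inside 4–8.

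**How often could a diary disagree with history? (Illustration, on an assumption.)** If 28-day counts were Poisson with a true rate between 4 and 8, 30% to 46% of patients would record a count outside 4–8. At 5.31 the figure is 22.4% below 4 plus 9.0% above 8 = 31%. Outside 4–14 it would be 6% to 43%. A Poisson SD at 5.31 is √5.31 = 2.30, above the reported 1.54 and 1.11. The reported counts were thus less variable than this, or were selected or taken from history, so the illustration is not an estimate for this trial.

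**The case against.** The strongest reply is that judging eligibility by history at Visit 1 and then recording a prospective baseline is a coherent design. The range is not tied to the diary, so a later count outside it would not make a patient ineligible as written. That stands: out of range here means only that the diary and the history disagree.

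Second, patient and investigator are blinded and no drug is taken in Weeks 0–4. If blinding holds, departures in that month cannot depend on allocation, so they cost numbers rather than validity. This also stands. A reader might infer that such patients must either be excluded, causing bias, or kept untreated, causing dilution. The documents do not support that, since nothing says a patient with a discordant diary is refused the drug. A reader might also infer that a covariate measured after allocation harms the analysis, but the plan is a t-test with no covariate.

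Third, the data suggest few early losses. Besides the means above, SAP Table 2 uses denominators of 17 and 16 for adverse events, which total all 33 (although the arm sizes are the reverse of those elsewhere). This bears on the realised size, not on the rule.

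Fourth, recruitment is never explicitly equated with Visit 1, and 87 patients were evaluated for 33 included, with no reasons for the other 54. Some screening during the diary month cannot be ruled out. Yet no text places allocation at Visit 2 or describes a diary check before it.

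Finally, the trial is complete, and completers would be selected by the elimination criteria wherever randomisation sat. Both are true. The first limits what can be done for this trial; the second is a separate matter.

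**Conclusion.** The point holds as a weakness in the plan as written, worth a cheap correction. Allocation at recruitment precedes diary return and first drug by four weeks without a described diary check. Patients lost or discordant in that month can enter the randomised set, and those who leave are then removed. The cost is avoidable post-randomisation loss and unconfirmed eligibility.

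A reader might go further and conclude that pre-treatment losses and out-of-range patients did enter. The documents do not show this: the six losses are undated, no patient is reported outside the range, and the baseline summaries are attainable with everyone inside 4–8. The size is bounded at 0 to 6 of 33 (0% to 18%), with the attack means favouring the low end.

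This rests on recruitment meaning Visit 1, on blinding having held, and, for the lean towards the low end, on whole-number baseline counts of uncertain source.

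**What to change.** Change the Work Plan so that randomisation takes place at Visit 2, after the baseline diary is collected and the attack count checked against the entry range, immediately before first dispensing. Reconcile the range first, since the Protocol gives 4–8 and the SAP 4–14, and state whether the diary count decides eligibility.

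The cost is about one sentence. Allocation must be ready at the Visit 2 dispensing, and some consented patients may never be randomised. No sample-size figure changes.

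The completed trial cannot be re-randomised. The report should state the visit at which randomisation actually occurred and how many of the six losses came before first drug, by arm. The revised wording would serve the larger trials that the Protocol's Limitations section calls for.

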Sample size calculation

Normal distribution model: $x=Z(c/100)^2 r(100-r)$. $n=Nx/((N-1)E^2+x)$ $E=\text{Sqrt}[(N-n)x/n(N-1)]$. With a margin of error of 5%, a confidence level of 95%, with a prevalence of migraine in the general population of the State of San Luis Potosi of 271800 with a distribution response of 15%.¹⁹ The recommended sample size is 196 participants. Due to the fact that a pilot study will be conducted, 10% of the sample size will be taken to make it representative, a sample size of 20 participants for each group is decided.²⁰

Descriptive statistical analysis of the variables of interest will be performed. For continuous variables, analysis will be performed using the Student's t-test. The number of participants (n) and the final analysis was calculated using R (56). Alpha, the probability of type 1 error was set to 0.05 and the power was set to 0.8 which resulted in the probability of a type 2 error of 0.2, given that we limited to 20 participants per treatment, delta was estimated with this restriction.

ETHICS

Risk category: Risk greater than minimal.

Authorization will be requested from the Research Ethics Committee of the Hospital Central "[name] Prieto". The study will be performed according to the Mexican Official Standard for the conduct of clinical studies in humans NOM-012-SSA3-2012²¹, and international standards (Declaration of Helsinki²² and International Harmonized Guide (ICH) of Good Clinical Practices²³) The diagnostic maneuvers that will be used are considered of higher than minimal risk because it is an interventional study according to article 17 of the regulations of the General Law of Health²³ on Health Research.

In addition, it is a priority to safeguard the physical and mental integrity of the patient, and privacy is respected by maintaining the confidentiality of the data at all times during the research, as well as the data obtained at the end of it. The consent of the legal subjects will be obtained through a document specifying the objective of the study, the duration, as well as the methods and medications that they will receive randomly.

RESULTS

Eighty-seven patients were evaluated, of which only 33 patients were included in the study. In the Memantine group with 16 patients and 17 in the Sodium Valproate (VPA) group; only 27 patients concluded the study.

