Migraine with aura	3 (18.75%)	4 (23.52%)

Secondary objectives. - Treatment response rate which is referred to as the decrease of equal or more than 50% of migraine days. In the Memantine group with pretreatment migraine days 4.3 (SD+ 1.93) and post treatment 0.23 (SD+ 0.44) with a mean decrease in migraine days of 3.9 (SD+ 1.89) $p <<0.001$. In the Sodium Valproate group with pretreatment migraine days 5.5 (SD+ 1.25) and post treatment 0.27 with mean decrease of migraine days 4.88 with (SD+ 1.29) $p <<0.001$ ([Figure](#))

4). In both groups the 27 patients presented a successful treatment response rate, in the Memantine group with a decrease in percentage of migraine days average 94% (SD+ 9.95) and in the Sodium Valproate group 93.18% (SD+ 14.50).

The intensity of migraine was evaluated with the Visual Analog Scale (VAS) pre and post treatment. In the Memantine group pre-treatment VAS 8.5 (SD+ 1.36) and post-treatment 4.28 (3.65) $p < 0.00014$. In the VPA group with pretreatment VAS 8.94(SD+ 0.87) and post treatment 2.5 (SD+ 0.87) $p < 0.0000012$.

Migraine disability assessed with MIDAS in the Memantine group with MIDAS mean pretreatment 60.87 (SD+ 25.22) and post-treatment 15.57 (SD+ 14.32) $p < 0.000004$. In the Sodium Valproate group with MIDAS pretreatment of 51.92 (SD+ 22.67) and post treatment 10.53 (SD+ 19.97) $p < 0.00002$ ([Figure 5](#)).

Figure 5. MIDAS pre- and post-treatment in both groups.

Side effects: The side effects presented by the patients were not severe in their totality, eight patients in the Memantine group presented non-severe side effects and seven patients in the sodium valproate group ([Table 2](#)), the most frequent in both groups being somnolence.

Table 2 . Side effects

	Memantine	Sodium Valproate
None		
Drowsiness		
Lack of concentration		0
Parasomnia	0	1
Dizziness		0
Total		

DISCUSSION

This is the first randomized double-blind pilot clinical trial comparing the efficacy and safety of memantine with a first-line treatment, sodium valproate.

With the objective of recruiting 40 patients as a pilot study, the Neurology outpatient clinic was suspended due to the COVID-19 pandemic, we finally managed to recruit 33 patients, 3 lost follow-up and 3 dropped out of the study due to COVID-19 and only 27 patients were included.

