Being a carrier of systemic disease (infectious, immunological, or metabolic processes) or cardiovascular (myocardial, coronary, or valvular disease) prevents their participation in the study.

Primary outcomes

The primary outcome was the difference in change from baseline in the monthly attack frequency at week 12 between the two groups (using migraine diary).

Secondary outcomes

1. Evaluate the response rate to treatment.
2. Evaluate migraine disability using MIDAS (Migraine Disability Assessment) before and after treatment.
3. Identify adverse effects to sodium valproate and memantine.

Statistical analysis.

Statistical analysis

Descriptive statistical analysis of the variables of interest will be carried out.

For continuous variables, their research will be analyzed using the t-student test.

First, the number of participants (n) and the final analysis were calculated using R (56).

Alpha, the probability of a type 1 error was set to 0.05.

The power was set to 0.8, resulting in a type 2 error of 0.2.

Since we were limited to 20 participants per treatment, the delta was estimated with this restriction.

Since we were limited to 20 participants per treatment, the delta was estimated with this restriction.

Results

Table 1. Baseline Demographic and Clinical Characteristics

[figure not shown]
Characteristic	Memantine	Sodium Valproate	p
Female sex – no (%)	13(81.25%)	13 (76.47%)	
Male sex – no (%)	3 (18.75%)	4 (23.52%)	0.54*
Age	$31.18 \pm 10.94^{\$}$	$31.58 \pm 7.51^{\$}$	0.91*
A family history of migraine (%)	10 (62.5%)	9 (52.94%)	0.82*
Clinical characteristics			
Photophobia - no (%)	14 (87.50%)	16 (94.12%)	0.48*
Phonophobia - no (%)	16 (100%)	10 (58.82%)	0.60*
Nausea - no (%)	14 (87.5%)	17 (100%)	0.23*
Disability activities of daily living	15 (93.75%)	16 (94.12%)	0.74*
Migraine without aura	13 (81.25%)	13 (76.47%)	0.54*
Migraine with aura	3 (18.75%)	4 (23.52%)	

* Fisher's exact test

§ Plus-minus values are means \pm SD

PRIMARY OUTCOME

[figure not shown]
Monthly attack migraine frequency before and after treatment

Secondary outcome

Evaluate the response rate to the treatment

Figure 2. Days with migraine before and after treatment

Adverse Events

Table 2. Adverse Events According to Group

	Memantine (n=17)	Sodium Valproate (n=16)	Clinical severity CTCAE*
Any adverse event	8	7	
Somnolence	4	6	Grade 1-Mild
poor concentration	2	0	Grade 1-Mild
Parasomnia	0	1	Grade 1-Mild
Dizziness	2	0	Grade 1-Mild

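### The 196 is a survey size for one proportion and does not size the two-group comparison; the 80% power is stated without a delta, an SD or sidedness

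*Protocol*

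**What the plan says.** The protocol (Statistical analysis, Sample size calculation) gives a formula with a 5% margin of error, 95% confidence, a population of 271,800 and a response distribution of 15%. It then states: "The recommended sample size is 196 participants". Because the study is a pilot, "10% of the sample size will be taken to make it representative, a sample size of 20 participants for each group is decided". The SAP's sample size section has the same derivation: "Because a pilot study will be conducted, 10% of the sample size will be taken to make it representative". The protocol Discussion confirms the overall target: "With the objective of recruiting 40 patients as a pilot study".

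The protocol then sets alpha at 0.05 and power at 0.8, and adds: "given that we limited to 20 participants per treatment, delta was estimated with this restriction". The SAP's Statistical analysis section says the same: "The power was set to 0.8, resulting in a type 2 error of 0.2" and "Since we were limited to 20 participants per treatment, the delta was estimated with this restriction". Continuous variables are to be analysed by Student's t-test.

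The comparison to be sized is given in the SAP under Primary outcomes: "The primary outcome was the difference in change from baseline in the monthly attack frequency at week 12 between the two groups".

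**The concern.** The formula is a precision formula for a survey. Its result is nevertheless called the recommended size for a randomised two-group trial whose primary outcome is a difference in mean change. The power statement that follows does concern a two-group test, but it lacks the quantities that would give it content. A reader cannot tell what difference in attacks per month the trial was meant to detect.

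This bears on how the result is read. The protocol's working hypothesis is that attack frequency on memantine is no higher than on valproate, and its Summary and Conclusions claim that memantine was not inferior. Neither document states a non-inferiority margin. A recommended 196, a 10% pilot fraction and 80% power, taken together, can suggest that the comparison behind that claim was sized, and the documents do not show that it was.

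**Working it through.** **1. Reproduce the 196.** Inputs from the protocol's Sample size calculation: E = 5, r = 15, N = 271,800, and Z = 1.96 for 95% confidence.

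- x = Z² · r · (100 − r) = 1.96² × 15 × 85 = 4898.04
- n = N·x / ((N − 1)·E² + x) = 271,800 × 4898.04 / (271,799 × 25 + 4898.04) = 195.78, rounded up to 196

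The arithmetic is right. The terms are one percentage, one margin of error, one confidence level and one population size. Number of arms, difference between arms, SD of change and power do not appear. The result answers how many people to sample to estimate a 15% proportion to within 5 points.

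**2. The 10% step.**

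- 0.10 × 196 = 19.6, about 20
- planned total = 2 × 20 = 40, and 40/196 = 20.4%

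The step agrees with 20 per group if the 10% is applied to each group, and does not if it is applied to the whole. The text does not say which was meant. On either reading it rescales a survey size and does not connect it to the t-test. The step carries a citation whose content cannot be seen here and is not judged.

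**3. The power statement.** Stated: alpha 0.05, power 0.8, 20 per treatment. Not stated in either document: delta, SD, sidedness. The 1.96 belongs to the survey formula and does not fix the sidedness of the t-test. The claimed power therefore cannot be reproduced. It can only be inverted, in SD units, for an unpaired t-test:

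- df = n₁ + n₂ − 2
- noncentrality = d · √(n₁n₂/(n₁ + n₂))
- solve for d so that P(T > t_crit) = 0.80 under the noncentral t

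| n₁ / n₂ | Sidedness at alpha 0.05 | df | t_crit | √(n₁n₂/(n₁+n₂)) | d for 80% power |
|---|---|---|---|---|---|
| 20 / 20 | two-sided | 38 | 2.024 | 3.162 | 0.909 |
| 20 / 20 | one-sided | 38 | 1.686 | 3.162 | 0.801 |
| 14 / 13 | two-sided | 25 | 2.060 | 2.596 | 1.123 |
| 14 / 13 | one-sided | 25 | 1.708 | 2.596 | 0.985 |

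The 14 and 13 are the completers reported in the protocol Summary. Both sidedness options are shown because neither document chooses one.

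**The case against.** The strongest defence is that the documents do not in fact claim that the t-test produced the sample size. They say that n was limited to 20 per treatment and that delta was estimated under that limit. Fixing n and reporting the detectable difference is a coherent approach for a pilot. The pilot label is plain in both documents, and the protocol admits the recruitment shortfall and calls for larger trials. All of that stands. It does not cure the point, because the estimated delta is not printed and the 196 is still called recommended.

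Four stronger readings are tempting, and the documents do not support them:

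- *The 10% step is an arithmetic error.* A reader might infer this from 19.6 against 40. Applied to each group, 19.6 rounds to 20, and no sentence says that the 10% is a total. The step is unclear, not shown to be wrong.
- *Twenty per group was simply a fixed pilot size.* The documents give two accounts, a 10% fraction and a limit of 20 per treatment, and do not settle which came first. The sponsor has to say.
- *Correcting the text lowers the planned power.* No delta was stated, so there is no stated performance to lower. The 0.91 SD is what 20 per group already implied.
- *The detectable difference can be put in attacks per month from the reported SDs of change.* Those SDs are results, not planning inputs. Post-treatment means of 0.93 and 0.77 with SDs of 1.49 and 1.16 also suggest a floor at zero. Such figures would not show what was planned and are not needed for the correction.

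The missing non-inferiority margin is a separate weakness that would remain after a perfect sample size section. It matters here only because it limits what a detectable difference can be used to claim.

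**Conclusion.** The point holds, as a fault in the choice of formula and in reporting. The 196 is computed correctly for one proportion and does not size the primary comparison. The 10% step does not bridge that gap, and the 80% power has no stated meaning in attacks per month.

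In size, 20 per group corresponds to about 0.91 SD two-sided or 0.80 SD one-sided. The 14 and 13 completers correspond to about 1.12 SD and 0.98 SD. The completer figures are larger only because fewer patients were available. These values assume two independent groups, equal variances, normally distributed changes and alpha 0.05.

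Without a margin, none of these figures supports a conclusion of no inferiority. They do not show that memantine is inferior either. The correction should be made, but it changes how the trial is described and leaves the data and the analysis as they are.

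**What to change.** Add a dated correction to the sample size sections of the protocol and the SAP, and to the repeated power text in the SAP's Statistical analysis section, leaving the existing text visible. Suggested wording:

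> The formula above gives the size for estimating one proportion (15% to within 5 points); neither it nor the 196 sizes the comparison of the two groups.

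The sponsor should then state how 20 per group was chosen, and report the delta, SD and sidedness used in R. If these cannot be recovered, say so and add:

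> With 20 per group a two-sample t-test has 80% power for a difference of about 0.91 SD at two-sided 0.05 (0.80 SD at one-sided 0.05); with the 14 and 13 completers this is about 1.12 SD (0.98 SD one-sided). No non-inferiority margin is stated, so these figures do not support a conclusion of no inferiority.

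The cost is a short note in three places and a search for the R inputs. No patients, design feature or analysis change, and the planned power at 20 per group is unaffected.
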